8.1. Treatment Groups

8. 1. 1 Placebo + Endovascular Treatment Group (Control Group)

After applying for randomization and obtaining the drug code, the medication box is quickly opened. The person opening the box signs the medication list, indicating the date and time of drug administration. The patient receives the placebo (methylprednisolone sodium succinate simulator), which is recommended to be administered before the establishment of arterial access and no later than 2 hours after the completion of endovascular treatment. The specific recommended usage of the methylprednisolone sodium succinate simulator (Chongqing Laimei Pharmaceutical Co., Ltd., 40mg) is: intravenous injection of 2mg/kg (maximum dose of 160mg), with the first dose administered before the procedure, once a day for three consecutive days. The endovascular interventional treatment methods include mechanical thrombectomy, contact aspiration, intra-arterial thrombolysis, balloon dilation, and/or emergency stent implantation. Details of the above treatments must be recorded in the CRF.

8. 1. 2 Methylprednisolone Sodium Succinate + Endovascular Treatment Group (Experimental Group)

After applying for randomization and obtaining the drug code, the medication box is quickly opened. The person opening the box signs the medication list, indicating the date and time of drug administration. The patient receives treatment with methylprednisolone sodium succinate, which is recommended to be administered before the establishment of arterial access and no later than 2 hours after the completion of endovascular treatment. The specific recommended usage of methylprednisolone sodium succinate (Chongqing Laimei Pharmaceutical Co., Ltd., 40mg) is: intravenous injection of 2mg/kg (maximum dose of 160mg), with the first dose administered before the procedure, once a day for three consecutive days. The endovascular interventional treatment methods include mechanical thrombectomy, contact aspiration, intra-arterial thrombolysis, balloon dilation, and/or emergency stent implantation. Details of the above treatments must be recorded in the CRF.

8.2. Concurrent Medications and Precautions

- Injectable methylprednisolone sodium succinate should not be used concurrently with live vaccines or attenuated live vaccines;
- During the trial treatment period, all used injectable methylprednisolone sodium succinate and corresponding simulators, as well as empty bottles and remaining medications, must be recovered after use.

8.3. Anesthesia Method

It is recommended to perform the procedure under intravenous sedation, and operators at sub-centers can also choose the anesthesia method independently based on the actual situation.

8.4. Cerebrovascular Angiography

To obtain comprehensive information that is conducive to endovascular treatment, aortic arch angiography is required. To embody the concept of "time is brain," the responsible vessel angiography for stroke can be performed first to clarify the characteristics of the lesion. After completing the endovascular treatment of the responsible vessel, other complex angiographies can be performed. When large artery occlusion is detected and thrombectomy is considered, it should be handled according to routine procedures.

8.5. Management of Patients Without Target Large Vessel Occlusion

In this study, if no large vessel occlusion is detected by DSA angiography, the surgeon should declare the end of the procedure without further intervention.

8.6. Management of Residual Stenosis

Arterial ischemic stroke can be classified into thrombotic stroke, embolic stroke, and combined stroke of both. Among them, thrombosis often develops secondary to stenosis. In this study, after successful thrombectomy, if >70% stenosis is found at the site of thrombosis formation, to further prevent re-occlusion after recanalization, the surgeon will decide whether to perform emergency stent implantation and other necessary measures after 10 minutes of observation.

9. Schedule of Assessments

Each patient, after signing the informed consent form, will undergo baseline examination, randomized group treatment study, and follow-up with mRS scoring at 90 days. The trial steps and items to be evaluated at each time point are listed in Table 1.

Table 1: Trial steps and items to be evaluated at each time point.

Evaluations/ Steps	Screening Treatm period ent period		ent	Follow up period	
	12h	12h~48h	2d~discharge	90 (±7) day	
Informed consent	X				
Demographic data	X				
Medical history	X				
Pre-stroke mRS	X				
Blood pressure and heart rate	X	X	X		
NIHSS score	X	X	Xa		
ASPECTS score	X				
mRS score				X	
EQ-5D score				X	
Blood routine examination	X				
Blood biochemistry	X		X		
Coagulation function	X				
Urine pregnancy test (women of childbearing age)	X				
Head CT/MRI and CTA/MRA/DSA	X				
ECG	X				
Inclusion/exclusion criteria	X				
Randomization	X				
Study medication ^b	X	X			
DSA Endovascular treatment		X			
Head CT/MRI		X			
Treatment medication		X		X	
Intracranial hemorrhage		X			
Adverse events		X	X	X	
Complications		X	X	X	
Completion status of clinical research				X	

Note: a5-7 days or at discharge (if hospital stay is <5 days); b2mg/kg, with a maximum of 160mg, administered consecutively for 3 days.

9.1. Collection of Baseline Data

Written informed consent must be obtained from the patient or their family members before implementing the research steps required by the protocol. The patient should be given a copy of the signed informed consent form to keep.

During the screening period, the following data should be evaluated and recorded in the original medical records and the single-disease database (intended to use the Yidu Cloud Scientific Research Collaboration Platform):

- 1) Patient information and informed consent form;
- 2) Evaluation of inclusion and exclusion criteria;
- 3) Demographic characteristics;
- 4) Past medical history and related treatment history;
- 5) For women of childbearing age: urine pregnancy test.

9.2. Randomized Group

After patients are screened and qualified, their randomized group information is obtained. Eligible patients are assigned to the experimental group and the control group in a 1:1 ratio.

During the treatment and visit periods, the following data should be evaluated and recorded in the original medical records and the Yidu Cloud Scientific Research Collaboration Platform:

- 1) Treatment method;
- 2) Neurological function assessment;
- 3) Laboratory test results such as blood routine, blood biochemistry, and coagulation function;
- 4) Imaging data such as CT/CTA/MRA/DSA;
- 5) Adverse reactions or events;
- 6) Study completion status.

9.3. Follow-up

The prognostic information of the patients was recorded in detail by two neurologists blinded to the treatment information within one week and 90 days after surgery. In case of inconsistent records between the two, the corresponding information was filled in the CRF after discussion and consensus.

Safety monitoring continued until 30 days after the end of follow-up. For patients who did not continue to participate in the study due to adverse reactions, follow-up should be conducted as far as possible until the adverse reactions were relieved or the condition was stable.

After the end of the trial, the follow-up treatment plan for patients with invalid or poor efficacy was implemented according to the Chinese Guidelines for the Secondary Prevention of Ischemic Stroke and Transient Ischemic Attack 2014.²⁸

10. Endpoints of the Clinical Trial

10.1. Primary Endpoints

10.1.1. Primary Efficacy Endpoint

Mortality at 90±7 days.

10.1.2. Primary Safety Endpoint

Proportion of patients with symptomatic intracranial haemorrhage (SICH) within 48 hours.

10.2. Secondary Endpoints

10.2.1. Secondary Efficacy Endpoints

- 1) mRS score improvement at 90 ±7 days;
- 2) Proportion of patients with mRS score 0 to 4 at 90 ± 7 days;
- 3) Proportion of patients with mRS score 0 to 3 at 90 \pm 7 days;
- 4) Proportion of patients with mRS score 0 to 2 at 90 ± 7 days;
- 5) Proportion of patients with mRS score 0 to 1 at 90 \pm 7 days;
- 6) mRS score improvement at 1 year;
- 7) Proportion of patients with mRS score 0 to 2 at 1 year;
- 8) Proportion of patients with mRS score 0 to 1 at 1 year;
- 9) mRS score improvement at 5 years;
- 10) Proportion of patients with mRS score 0 to 2 at 5 years;
- 11) Proportion of patients with mRS score 0 to 1 at 5 years;
- 12) NIHSS score at 5-7 days or at early discharge;
- 13) Health-related quality of life [European Quality of Life Five-Dimension visual-analogue scale (EQ-5D VAS)] at 90 ± 7 days;
- 14) Proportion of patients with malignant cerebral edema within 48 hours after EVT
- 15) Proportion of patients with secondary decompressive craniectomy
- 16) EQ-5D VAS at 1 year
- 17) EQ-5D VAS at 5 years

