Intravascular therapy helps improve the prognosis of patients with acute ischemic stroke, but postoperative complications such as hemorrhagic transformation and malignant brain edema are important causes of death. Hemorrhagic transformation refers to the hemorrhage in the ischemic lesion caused by a variety of underlying mechanisms during ischemic stroke, among which the incidence of hemorrhagic transformation after intravascular treatment is about 46%-49.5%, and the incidence of symptomatic hemorrhagic transformation is 2%-16%. He is currently believed that oxidative stress, inflammatory response, and blood-brain barrier damage may be the underlying mechanisms of hemorrhagic transformation after intravascular treatment of acute ischemic stroke. Malignant cerebral edema is the main cause of early death and disability after ischemic stroke, with an incidence of 10%-78% in patients with ischemic stroke. It is characterized by a malignant course accompanied by severe cerebral edema, leading to cerebral hemia, death, or severe neurological dysfunction. The main mechanisms of cerebral edema after ischemic stroke include early cytotoxic edema and late vasogenic edema. Early cytotoxic edema is due to increased permeability of brain tissue and failure of Na+/K+ pump caused by ischemia and hypoxia, resulting in cell swelling, narrowing of extracellular space, and increased brain volume. Tissue necrosis and basement membrane degeneration cause damage to the blood-brain barrier, and 4-6 hours later, serum proteins begin to enter the brain from the blood,

inducing vasogenic edema and further increasing brain water content. In addition, reperfusion of the blood supply artery in the infarct area leads to more water passing through the damaged blood-brain barrier, combined with ischemia-reperfusion and hyperperfusion injury after mechanical thrombectomy, further exacerbating vasogenic edema, which peaks 1 to several days after ischemia and leads to malignant cerebral edema. Therefore, reducing complications such as hemorrhagic transformation and malignant cerebral edema after intravascular therapy is the key to ultimately reducing the mortality rate of patients with acute ischemic stroke.

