4.4. Privacy Protection

completely stored in the hospital where they receive treatment, and laboratory test reports and other examination results will be recorded in the patients' medical records. Only the investigators, ethics committees, and food and drug administration departments of this study will be allowed to access patients' medical records. Any public reports on the results of this study will not disclose the personal identities of patients. We will make every effort to protect the privacy of patients' personal medical information within the limits allowed by law.

According to medical research ethics, apart from personal privacy information, trial data will be available for public inquiry and sharing. Inquiry and sharing will be limited to web-based electronic databases to ensure that no personal privacy information is leaked.

5. Sample Size Calculation

Based on the research results from published literature and combined with clinicians' experience, the 90-day mortality rates for the intravenous methylprednisolone sodium succinate + endovascular treatment group (experimental group) and the placebo + endovascular treatment group (control group) are estimated to be 29% and 38%, respectively. Assuming a 1:1 ratio for the sample sizes of the two groups, a two-sided α of 0.05, and a power of 80%, the estimated sample size is 856 patients. Considering an expected dropout rate of 5%, the maximum estimated sample size, calculated using PASS 15.0, is 902 patients, with 451 patients in each of the intravenous methylprednisolone sodium succinate + endovascular treatment group (experimental group) and the placebo + endovascular treatment group (control group).

6. Randomization

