12.2.4. Missing Data

12.3. Statistical Analysis Methods

Statistical tests will be performed using a two-sided significance level of 0.05 for indicators evaluated with superiority. Differences with a P-value ≤ 0.05 will be considered statistically significant.

Statistical analysis will be conducted on baseline indicators (such as medical history) and demographic characteristics. Intent-to-treat analysis will be used for statistical analysis of trial efficacy, with the per-protocol dataset (i.e., data from patients who meet all trial protocol criteria) as a reference.

Quantitative data will be described using means, medians, standard deviations, maximum and minimum values, and 25th and 75th percentiles. Comparisons between two groups will be made using the independent t-test or Mann-Whitney U test. Categorical or ordinal data will be described using frequencies and proportions. Comparisons between two groups for categorical data will be made using the chi-square test or Fisher's exact test, and for ordinal data, the Mann-Whitney *U* test will be used.

Previous studies have suggested that the following factors may affect the 90-day mRS score, and this study plans to conduct subgroup analysis based on these variables.

- 1) Age;
- 2) Gender:
- 3) Time of onset;
- 4) NIHSS score:
- 5) ASPECTS score;
- 6) TOAST classification [22];
- 7) Vascular occlusion site;
- 8) Collateral circulation score:
- 9) Anesthesia method:
- 10) Intravenous thrombolysis.

13. Quality Control and Assurance

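### Secondary decompressive craniectomy (item 15) has no time window and no handling of death, so a patient who dies unoperated counts as a favourable result on that endpoint

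*Combined protocol and SAP*

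**What the plan says.** Item 15 of the secondary efficacy endpoints (Section 10.2.1, repeated in the synopsis) reads "Proportion of patients with secondary decompressive craniectomy". Neither place adds a time limit, a denominator or a rule for patients who die. Item 14, directly above it, does have a window: "Proportion of patients with malignant cerebral edema within 48 hours after EVT".

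On the test, Section 12.3 says "Comparisons between two groups for categorical data will be made using the chi-square test or Fisher's exact test". No competing-risk method and no composite with death appears. The heading for Section 12.2.4 (Missing Data) has no text under it.

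The analysis sets do not settle the matter. Section 12.2.1 removes from the FAS randomised patients who were not treated or have no evaluation results. Section 12.2.2 assigns all secondary indicators to the PPS. Section 12.3 calls for intention-to-treat analysis of efficacy, with the per-protocol data as a reference. None of them mentions death before surgery.

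Death is counted separately, as the primary efficacy endpoint: "Mortality at 90±7 days". Section 5 gives 90-day mortality on experimental and control treatment, which "are estimated to be 29% and 38%, respectively". The background (Section 1) states that "Malignant cerebral edema is the main cause of early death and disability after ischemic stroke".

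**The concern.** Because item 15 is listed under efficacy, a lower craniectomy rate will be taken as benefit. Death rules the operation out. By the plan's own account, malignant edema is a leading cause of early death, so operation and unoperated death are alternative ends of the same process. In a plain proportion, the patient who dies unoperated falls in the same cell as the patient who never needed surgery. Dropping such patients would confine the comparison to patients selected by survival, which the treatment is expected to change. The plan chooses neither course explicitly.

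What is at stake is the interpretation of one endpoint. If the drug keeps some patients alive long enough to be operated on, those operations count against it on item 15. A null or adverse result there could then stand beside a mortality benefit with no planned display to explain it.

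**Working it through.** **Inputs from the documents.** Mortality 38% control and 29% experimental; two-sided 0.05; 80% power; 1:1 allocation; 856 patients before dropout and 902 after 5% dropout (all Section 5). Chi-square or Fisher's exact test (Section 12.3).

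**Inputs that the documents do not give.** The proportion of patients who come to need craniectomy, and the share of those who die unoperated. Both are assumed and varied below.

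**Step 1: reproduce the plan's figure.** With unpooled variance, n per arm = (1.960 + 0.842)² × (0.38 × 0.62 + 0.29 × 0.71) / 0.09² = 427.8, so 428 per arm and 856 in total, as stated. With dropout, 428 / 0.95 = 450.5, so 451 per arm and 902 in total, as stated. Power for all comparisons below, with n = 428 per arm, is

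Φ{ [ |p₁ − p₂| − 1.96 √(2 p̄(1 − p̄)/n) ] / √[ (p₁(1 − p₁) + p₂(1 − p₂))/n ] }.

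For 38% v 29% it gives 79.8%, in line with the planned 80%.

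**Step 2: how many deaths.** 428 × 0.38 ≈ 163 control deaths and 428 × 0.29 ≈ 124 experimental deaths by day 90. These are deaths from all causes. Only those that occur without prior craniectomy, in patients who would otherwise have had it, compete with item 15.

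**Step 3: the model.** Let q be the proportion who come to need craniectomy and s the share of those who are operated on; the rest die unoperated. The observed craniectomy rate is q × s, so

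observed risk ratio = (q_drug / q_control) × (s_drug / s_control).

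The first factor is the effect on need. The second is the distortion, and it equals 1 when the operated share is the same in both arms.

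**Step 4: scenarios** (assumed; control s = 50%; effect on need 0.76, which is 29/38 rounded, or none).

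| Need, control v drug | Operated share, control v drug | Craniectomy, control v drug | Risk ratio | Power |
|---|---|---|---|---|
| 30% v 22.8% | 50% v 50% | 15.0% v 11.4% | 0.76 | 34% |
| 30% v 22.8% | 50% v 60% | 15.0% v 13.7% | 0.91 | 8% |
| 30% v 22.8% | 50% v 66% | 15.0% v 15.0% | 1.00 | no effect left |
| 30% v 30% | 50% v 60% | 15.0% v 18.0% | 1.20 | apparent harm, 3 points |
| 20% v 15.2% | 50% v 50% | 10.0% v 7.6% | 0.76 | 24% |
| 20% v 15.2% | 50% v 60% | 10.0% v 9.1% | 0.91 | 6% |

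The effect vanishes when s_drug = 0.50 / 0.76 = 0.66 and reverses above that.

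**Step 5: a second set of assumptions.** Take need of 20% v 15%, with 50% of control patients in need dying unoperated. If 50%, 40% or 30% of drug patients in need die unoperated, craniectomy reads 10.0% v 7.5%, 9.0% or 10.5%. A true 5-point reduction in need therefore shows as 2.5 points, 1.0 point, or 0.5 points in the wrong direction. The pattern matches Step 4.

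**The case against.** The strongest reply has four parts.

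- **The score is not wrong.** An unoperated death is correctly recorded as not operated. In all randomised patients, the proportion compares operation rates as they occurred. This stands: the flaw lies in reading that rate as efficacy with nothing beside it. Scoring deaths this way is also the default reading, not a written rule. Section 12.1.1 leaves derivations to a SAP to be finalised before database lock, so the gap can still be closed.
- **The size is assumed.** This also stands. The 38% and 29% are all deaths, not unoperated ones. In the 30% scenario, 15% of controls die unoperated, which leaves 38 − 15 = 23 points for deaths after surgery or from other causes, and the documents do not give this split. The shift from 50% to 60% operated has no source in them either. More deaths on control do not by themselves bias the risk ratio; an unequal operated share does.
- **Lower power alone is not bias.** In the 30% scenario with equal shares, craniectomy or unoperated death (30.0% v 22.8%) has 67% power against 34% for craniectomy alone, but both risk ratios are 0.76. The gap reflects the number of events, so it is not used here as evidence of distortion.
- **The plan does not lean on item 15 alone.** Item 14 measures malignant edema directly, and no section states what item 15 is meant to show. This limits the importance of the point but does not supply the missing rule.

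**Conclusion.** The point holds for item 15 only. As written, the endpoint has no window and no handling of death, and an unoperated death falls on the favourable side. The difference can shrink, vanish or reverse if the share of patients in need who die unoperated differs between arms. If that share is equal, the relative effect is intact. The illustration of 15.0% v 13.7% (risk ratio 0.91, power about 8%) rests on assumed values: 30% need in controls, a true risk ratio of 0.76, and 50% v 60% operated. It is not a forecast.

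A reader might infer that a life-saving drug could look ineffective in this trial. The documents do not support that: 90-day mortality is the primary endpoint and the mRS endpoints are reported as well, so a survival benefit would not be hidden by item 15. Nor do they support a claim that the result will be biased, since nothing in them shows that the operated share will differ. This is a worthwhile, low-cost improvement and not a threat to the main conclusion.

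**What to change.** In Section 10.2.1, the synopsis and the SAP:

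1. Give item 15 a fixed time window. The documents offer no basis for a particular one, so the sponsor should choose and justify it before unblinding.
2. Analyse it in all randomised patients, and reconcile this with Section 12.2.1, which excludes some of them, and Section 12.2.2, which assigns secondary indicators to the PPS.
3. Report craniectomy and death without craniectomy side by side by arm. Either treat death as a competing event (cumulative incidence) or add death or craniectomy as a supporting composite.
4. State that craniectomy alone will not be read as evidence of efficacy.

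The cost is small: wording and slightly more analysis. Dates of operation and death must be captured; Table 1 has no row for craniectomy and the complication lists in Section 10.2.2 do not name it, so the CRF should be checked. Any composite shares its deaths with the primary endpoint and so adds less independent evidence. That is a reason to keep it supporting and to show the components.

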10.2.2. Secondary Safety Endpoints

- Proportion of patients with asymptomatic intracranial haemorrhage (aSICH) within 48 hours after EVT; 1)
- 2) The incidence of non-intracranial hemorrhage complications (including gastrointestinal bleeding, urethral bleeding, oral or nasal mucosal bleeding, and subcutaneous hematoma, etc.);
- The incidence of non-hemorrhagic serious adverse events (including cerebral hernia, pneumonia, respiratory failure, circulatory failure, stress ulcer, secondary epilepsy, urinary tract infection, sepsis, renal failure, acute coronary syndrome, venous thrombosis, and psychiatric symptoms, etc.);
- 4) Operation and device-related complications (including artery rupture, artery dissection, implant failure, stent

Release date: July 23, 2024

fracture, vascular puncture site complications, vasospasm, and device not in place, etc.);

5) Glucocorticoid-related adverse events (including insulin use in hospital, new-onset diabetes, lung infection during hospitalization, gastrointestinal bleeding within 7 days after surgery, etc.).

11. Adverse Events

